5. TREATMENT PLAN

This is a single arm, multicenter phase II trial for 60 patients with untreated extensive stage (ES) small cell lung cancer (SCLC) with asymptomatic brain metastases. Subjects will receive 4 cycles of induction treatment with Atezolizumab (1200 mg on Day 1) combined with carboplatin (5-6 AUC on Day 1) and etoposide (80-100 mg/m² on Days 1-3). Each cycle equals 21 days. After 4 cycles of induction treatment, subjects will receive atezolizumab maintenance 1200 mg on Day 1 of each 3-week cycle. Subjects will receive treatment until disease progression, unacceptable drug-related toxicity, or withdrawal from study for any reason.

5.1 Study Treatment

5.1.1 ACE (Atezolizumab-Carboplatin-Etoposide) Induction

Drug	Dose ¹	Route	Schedule ²	Cycle Length	Total # of Cycles
Atezolizumab	1200 mg	Intravenously (IV) over 60 minutes before carboplatin	Day 1	3 weeks (21 days)	4
Carboplatin	5-6 mg/mL/min AUC	IV over 30-60 min after completion of atezolizumab	Day 1		
Etoposide	80-100 mg/m ²	IV over 60 min after completion of carboplatin	Days 1, 2, 3		

¹ Dosing calculations should be based on actual body weight where applicable. Institutional standards for recalculating the dose based on weight changes should be used. All doses should be rounded up or to the nearest milligram per institutional standard.

² A window of ± 3 days may be applied to all study visits to accommodate observed holidays, inclement weather, scheduling conflicts etc. Date and time of each drug administration should be clearly documented in subject's chart and electronic case report forms (eCRFs).

5.1.2 Atezolizumab Maintenance

Drug	Dose	Route	Schedule ¹	Cycle Length
------	------	-------	-----------------------	--------------

Atezolizumab	1200 mg	IV over 60 minutes	Day 1	3 weeks (21 days)
¹ A window of \pm 7 days may be applied to all study visits to accommodate observed holidays, inclement weather, scheduling conflicts etc. Date and time of each drug administration should be clearly documented in subject's chart and electronic case report forms (eCRFs).				

5.2 Chemotherapy

Institutional standards may be used for the infusion of carboplatin and etoposide. This includes pre-medications, infusion windows and treatment of side effects. Because the effects of corticosteroids on T-cell proliferation have the potential to attenuate atezolizumab-mediated anti-tumor immune activity, premedication with corticosteroids should be minimized to the extent that is clinically feasible. The current package insert should be referenced for additional information regarding these medications. Both medications will be used in the commercially available formulation.

5.2.1 Carboplatin

Carboplatin 5-6 mg/mL/min AUC will be delivered over 30 - 60 minutes intravenously on Day 1 of each 21 day Cycle after completion of atezolizumab. Institutional standards may be used for dose calculation.

5.2.2 Etoposide

Etoposide 80-100 mg/m²² will be delivered over 60 minutes intravenously on Days 1-3 of each 21 day Cycle after completion of carboplatin (Day 1 only). Institutional standards may be used for dose calculation.

5.3 Atezolizumab

Atezolizumab 1200 mg will be delivered over 60 (\pm 15) minutes intravenously on Day 1 of each 21 day Cycle. Institutional standards may be used regarding all aspects of the infusion. The investigator's brochure should be utilized for additional details regarding this medication.

Administration of atezolizumab will be performed in a monitored setting where there is immediate access to trained personnel and adequate equipment and medicine to manage potentially serious reactions. Atezolizumab infusions instructions outlined in the Table below.

First Infusion	Subsequent Infusions

 • No premedication is allowed. • Record patient's vital signs (heart rate, respiratory rate, blood pressure, and temperature) within 60 minutes before starting infusion. • Infuse atezolizumab (1200 mg in a 250 mL 0.9% NaCl intravenous infusion bag) over 60 (\pm 15) minutes. • If clinically indicated, record patient's vital signs (heart rate, respiratory rate, blood pressure, and temperature) during the infusion at 15, 30, 45, and 60 minutes 	
 • If the patient experienced an infusion-related reaction during any previous infusion, premedication with antihistamines may be administered for Cycles \geq 2 at the discretion of the treating physician. • Record patient's vital signs (heart rate, respiratory rate, blood pressure, and temperature) within 60 minutes before starting infusion. • If the patient tolerated the first infusion well, without infusion-associated adverse events,


 (\pm 5-minute windows are allowed for all time points). If clinically indicated, record patient's vital signs (heart rate, respiratory rate, blood pressure, and temperature) at 30 (\pm 10) minutes after the infusion. Patients will be informed about the possibility of delayed post-infusion symptoms and instructed to contact their study physician if they develop such symptoms. 	
 the second infusion may be administered over 30 (\pm 10) minutes. If no reaction occurs, subsequent infusions may be administered over 30 (\pm 10) minutes. 
 Continue to record vital signs within 60 minutes before starting infusion and during and after the infusion, if clinically indicated. If the patient had an infusion-related reaction during the previous infusion, the subsequent infusion must be administered over 60 (\pm 15) minutes. 
 Record patient's vital signs (heart rate, respiratory rate, blood pressure, and temperature) during the infusion if clinically indicated or if patient experienced symptoms during the previous infusion. Record patient's vital signs (heart rate, respiratory rate, blood pressure, and temperature) 30 (\pm 10) minutes after the infusion if clinically indicated or if patient experienced symptoms during previous infusion.
---	--

5.3.1 Infusion -Related Reactions with Atezolizumab

No premedication is indicated for the administration of Cycle 1 of atezolizumab. However, patients who experience an infusion-related reaction (IRR) with Cycle 1 of atezolizumab may receive premedication with antihistamines or antipyretics/analgesics (e.g., acetaminophen) for subsequent infusions. Metamizole (dipyrone) is prohibited in treating atezolizumab-associated IRRs because of its potential for causing agranulocytosis. Guidelines for medical management of IRRs during Cycle 1 are provided in the Table below. For subsequent cycles, IRRs should be managed according to institutional guidelines.

5.3.2 Management Guidelines for Infusion-Related Reactions

Event	Management
IRR, Grade 1	
 Reduce infusion rate to half the rate being given at the time of event onset. After the event has resolved, the investigator should wait for 30 minutes while delivering the infusion at the reduced rate. If the infusion is tolerated at the reduced rate for 30 minutes after symptoms have resolved, the infusion rate may be increased to the original rate. Monitor vital signs as clinically indicated
IRR, Grade 2	
 Interrupt atezolizumab infusion. Administer aggressive symptomatic treatment (e.g., oral or IV antihistamine, anti-pyretic medication, glucocorticoids, epinephrine, bronchodilators, oxygen). After symptoms have resolved to baseline, resume infusion at half the rate being given at the time of event onset.

	
 For subsequent infusions, consider administration of oral premedication with antihistamines, anti-pyretics, and/or analgesics and monitor closely for IRRs. Monitor vital signs as clinically indicated Consider permanent discontinuation of atezolizumab treatment if Grade 2 infusion reaction occurs despite adequate premedication
IRR, Grade 3 or 4	
 Stop infusion. Administer aggressive symptomatic treatment (e.g., oral or IV antihistamine, anti-pyretic, glucocorticoids, epinephrine, bronchodilators, oxygen). Monitor vital signs as clinically indicated Hospitalization indicated for clinical sequelae (examples: renal impairment, pulmonary infiltrates) Permanently discontinue atezolizumab.^a

IRR = infusion-related reaction.

^a Resumption of atezolizumab may be considered in patients who are deriving benefit and have fully recovered from the immune-related event. Patients can be re-challenged with atezolizumab only after approval has been documented by the investigator (or an appropriate delegate). See Appendix I for additional information.

5.4 Concomitant Medications

Concomitant therapy includes any medication (e.g., prescription drugs, over-the-counter drugs or homeopathic remedies, nutritional supplements) used by a patient from 7 days prior to screening until the treatment discontinuation visit. Steroid medication use should be reported to the investigator and recorded on the Concomitant Medications eCRF.

5.4.1 Allowed Concomitant Medications

All treatments that the investigator considers necessary for a subject's welfare may be administered at the discretion of the investigator in keeping with the community standards of medical care.

The following therapies may continue while patients are in the study:

- Oral contraceptives
- Hormone-replacement therapy
- Prophylactic or therapeutic anticoagulation therapy (such as low molecular weight heparin or warfarin at a stable dose level)
- If palliative radiotherapy is required, it should be discussed with HCRN and the sponsor-investigator.
- Inactive influenza vaccinations
- Megestrol administered as an appetite stimulant
- Inhaled corticosteroids for chronic obstructive pulmonary disease
- Mineralocorticoids (e.g., fludrocortisone)
- Low-dose corticosteroids for patients with orthostatic hypotension or adrenocortical insufficiency

In general, investigators should manage a patient's care with supportive therapies as clinically indicated per local standards. Patients who experience infusion-associated symptoms may be treated symptomatically with acetaminophen, ibuprofen, diphenhydramine, and/or famotidine or another H2 receptor antagonist per standard practice (for sites outside the United States,

equivalent medications may be substituted per local practice). Serious infusion-associated events manifested by dyspnea, hypotension, wheezing, bronchospasm, tachycardia, reduced oxygen saturation, or respiratory distress should be managed with supportive therapies as clinically indicated.

All concomitant steroid medications must be recorded on the appropriate Concomitant Medications eCRF.

5.4.2 Cautionary Therapy for Atezolizumab-Treated Patients

Systemic corticosteroids and TNF- α inhibitors may attenuate potential beneficial immunologic effects of treatment with atezolizumab. Therefore, in situations where systemic corticosteroids or TNF- α inhibitors would be routinely administered, alternatives, including antihistamines, should be considered first by the treating physician. If the alternatives are not clinically appropriate, systemic corticosteroids and TNF- α inhibitors may be administered at the discretion of the treating physician except in the case of patients for whom CT scans with contrast are contraindicated (i.e., patients with contrast allergy or impaired renal clearance).

Systemic corticosteroids are recommended, with caution, at the discretion of the treating physician, for the treatment of specific adverse events when associated with atezolizumab therapy.

Refer to the Atezolizumab Investigator's Brochure for additional information on the management of immune-mediated adverse events.

5.4.3 Prohibited Concomitant Medications with Atezolizumab

Any concomitant therapy intended for the treatment of cancer, whether health authority-approved or experimental, is prohibited for various time periods prior to starting study treatment, depending on the anti-cancer agent, and during study treatment until disease progression is documented and the patient has discontinued study treatment. This includes, but is not limited to chemotherapy, hormonal therapy, immunotherapy, radiotherapy, non-approved experimental agents, or herbal therapy (unless otherwise noted).

The following medications are prohibited while in the study, unless otherwise noted:

- Denosumab; patients who are receiving denosumab prior to enrollment must be willing and eligible to receive a bisphosphonate instead
- Any live, attenuated vaccine (e.g., FluMist®) within 4 weeks prior enrollment, during treatment, and for 5 months following the last dose of atezolizumab
- Use of steroids to premedicate patients for whom CT scans with contrast are contraindicated (i.e., patients with contrast allergy or impaired renal clearance); in such patients, non-contrast CT scans of the chest and non-contrast CT scans or MRIs of the abdomen and pelvis should be performed

The concomitant use of herbal therapies is not recommended because their pharmacokinetics, safety profiles, and potential drug-drug interactions are generally unknown. However, their use for patients in the study is allowed at the discretion of the investigator, provided that there are no

known interactions with any study treatment. As noted above, herbal therapies intended for the treatment of cancer are prohibited.

5.5 Supportive Care

In general, investigators should manage a patient's care with supportive therapies as clinically indicated per local standards. Patients who experience infusion-associated symptoms may be treated symptomatically with acetaminophen, ibuprofen, diphenhydramine, and/or famotidine or another H2 receptor antagonist per standard practice (for sites outside the United States, equivalent medications may be substituted per local practice). Serious infusion-associated events manifested by dyspnea, hypotension, wheezing, bronchospasm, tachycardia, reduced oxygen saturation, or respiratory distress should be managed with supportive therapies as clinically indicated.

All concomitant steroid medications must be recorded on the appropriate Concomitant Medications eCRF.

5.6 Reproductive Information

Negative pregnancy test done \leq 72 hours (or per institutional policy) prior to treatment, for women of childbearing potential only. Female subjects should be using highly effective contraceptive measures, and must have a negative pregnancy test or must have evidence of non-child-bearing potential by fulfilling one of the following criteria at screening:

- Post-menopausal defined as aged more than 50 years and amenorrheic for at least 12 months following cessation of all exogenous hormonal treatments.
- Women under 50 years old would be considered postmenopausal if they have been amenorrheic for 12 months or more following cessation of exogenous hormonal treatments and with LH and FSH levels in the post-menopausal range for the institution
- Documentation of irreversible surgical sterilization by hysterectomy, bilateral oophorectomy or bilateral salpingectomy but not tubal ligation

Men and women of childbearing potential must agree to use highly effective methods of contraception, including at least one method with a failure rate of $< 1\%$ per year, during the course of the study and for 5 months after the last dose of study drug, even if oral contraceptives are also used. All subjects of reproductive potential must agree to use both a barrier method and a second method of birth control during the course of study and for 5 months after the last dose of study drug.

5.6.1 Contraception Options

Highly effective methods of contraception, defined as one that results in a low failure rate (i.e., less than 1% per year) when used consistently and correctly are described in the table below. Note that some contraception methods are not considered highly effective (e.g. male or female condom with or without spermicide; female cap, diaphragm, or sponge with or without spermicide; non-copper containing intrauterine device; progestogen-only oral hormonal contraceptive pills where inhibition of ovulation is not the primary mode of action; and triphasic combined oral contraceptive pills). Abstaining from heterosexual intercourse is considered an effective method of contraception.

Highly Effective Methods of Contraception (<1% Failure Rate)

Barrier/Intrauterine methods	Hormonal Methods
• Copper T intrauterine device	• Etonogestrel implants: e.g. Implanon
• Levonorgestrel-releasing intrauterine system (e.g., Mirena®) ^a	• Intravaginal device: e.g. ethinylestradiol and etonogestrel
	• Medroxyprogesterone injection: e.g. Depo-Provera
	• Normal and low dose combined oral contraceptive pill
	• Norelgestromin/ethinylestradiol transdermal system

^a This is also considered a hormonal method

6. TOXICITIES AND DOSE DELAYS/DOSE MODIFICATIONS

The NCI Common Terminology Criteria for Adverse Events (CTCAE) v5 will be used to grade adverse events. Subjects enrolled in this study will be evaluated clinically and with standard laboratory tests before and at regular intervals during their participation in this study as specified in Study Calendar & Evaluations. Subjects will be evaluated for adverse events (all grades), serious adverse events, and adverse events requiring study drug interruption or discontinuation as specified in Study Calendar & Evaluations.

6.1 Dose Delays/Dose Modifications

Reasons for dose modifications including dose delays, the supportive measures taken, and the outcomes will be documented in the patient's chart and recorded on the eCRF. The severity of adverse events will be graded according to the NCI CTCAE v5 grading system.

- When several toxicities with different grades of severity occur at the same time, the dose modifications should be according to the highest grade observed.
- If, in the opinion of the investigator, a toxicity is considered to be due solely to one component of the study treatment and the dose or administration of that component is delayed or modified, the dose or administration of the other study treatment components do not require modification and may be administered if there is no contraindication.
- When treatment is temporarily interrupted because of toxicity caused by atezolizumab, carboplatin, or etoposide, the treatment cycles should be restarted such that the atezolizumab infusions remain synchronized and aligned with the chemotherapy schedule.
- If, in the opinion of the investigator, a toxicity is considered to be due solely to one chemotherapy drug, the dose of the other chemotherapy drug does not require modification.

The investigator may use discretion in modifying or accelerating the dose modification guidelines described below depending on the severity of toxicity and an assessment of the risk versus benefit for the patient, with the goal of maximizing patient compliance and access to supportive care.

6.2 Atezolizumab Dose Modification

There will be no dose modifications for Atezolizumab. Adverse events will be managed as described in detail in Appendix “Management of Atezolizumab-Specific Adverse Events”.

If a dose of atezolizumab is withheld for toxicity, then subjects may resume dosing with atezolizumab if that is appropriate at their next scheduled appointment or when toxicity has improved as described in the Appendix “Management of Atezolizumab-Specific Adverse Events”.

Atezolizumab will be withheld for drug-related Grade 4 hematologic toxicities, non-hematological toxicity \geq Grade 3 including laboratory abnormalities, and severe or life-threatening AEs as below and as listed in appendix.

Subjects who require corticosteroids to manage atezolizumab-related AEs must be at an equivalent dose of \leq 10 mg per day of prednisone to resume dosing with atezolizumab. Furthermore, an inability to reduce the corticosteroid dose for managing a drug-related adverse event to the equivalent of \leq 10 mg prednisone per day within 12 weeks of the last atezolizumab dose should prompt discussion between the site investigator and sponsor-investigator regarding the subject’s ability to continue on treatment with atezolizumab the study. With site investigator and sponsor-investigator agreement, subjects with a laboratory adverse event still at Grade 2 after 12 weeks may continue treatment in the study only if asymptomatic and controlled.

In subjects who continue on atezolizumab having experienced a Grade 3, Grade 4, or persistent ($>$ 4 weeks) Grade 2 atezolizumab-related AE, dosing should be held until the AE resolves to Grade 0-1 or baseline.

However, in subjects who experience Grade 3 or 4 pneumonitis, or recurrent persistent ($>$ 4 weeks) Grade 2 drug-related pneumonitis after re-challenge from a prior episode of persistent ($>$ 4 weeks) Grade 2 drug-related pneumonitis, atezolizumab must be permanently discontinued.

For subjects Hepatotoxicity events of Grade 3-4, patients are to permanently discontinue Atezolizumab, with the exception of patients with liver metastasis who began treatment with Grade 2 AST or ALT; if AST or ALT increases by greater than or equal to 50% relative to baseline and lasts for at least 1 week then subjects should be discontinued.

Subjects with intolerable or persistent Grade 2 drug-related AE may hold study medication at physician discretion. Permanently discontinue study drug for persistent Grade 2 adverse reactions for which treatment with study drug has been held, that do not recover to Grade 0-1 within 12 weeks of the last dose.

Refer to the Atezolizumab Investigator's Brochure for more detailed information regarding dose modification.

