3. ELIGIBILITY CRITERIA

3.1 Inclusion Criteria

Subject must meet all of the following applicable inclusion criteria to participate in this study:

1. Written informed consent and HIPAA authorization for release of personal health information prior to registration. **NOTE:** HIPAA authorization may be included in the informed consent or obtained separately.
2. Age \geq 18 years with ability and willingness to provide informed consent.
3. ECOG Performance Status of 0-2.
4. Histological confirmation of Small Cell Lung Cancer- Extensive Stage (SCLC) per Veterans Administration Lung Study Group (VALG).
5. At least one untreated asymptomatic brain metastasis that is measurable by RECIST 1.1 that has not been previously irradiated.
6. No prior treatment for metastatic disease. **EXCEPTION:** A single cycle of chemotherapy (platinum/etoposide) with or without atezolizumab is allowed within 30 days prior to enrollment.
7. Treatment-free for at least 6 months since last chemo/radiotherapy, among those treated (with curative intent) with prior chemo/radiotherapy for limited-stage SCLC.
8. Any prior cancer treatment must be completed at least 6 months prior to registration and the subject must have recovered from all reversible acute toxic effects of the regimen (other than alopecia) to Grade \leq 1 or baseline. **NOTE:** a single cycle of chemotherapy (platinum/etoposide) with or without atezolizumab is allowed within 30 days prior to enrollment. **NOTE: Extracranial radiation is allowed.**
9. A concurrent diagnosis of a separate malignancy is allowed if clinically stable and does not require tumor-directed therapy.

10. Demonstrate adequate organ function as defined in the table below

System	Laboratory Value
Hematological	
Absolute Neutrophil Count (ANC)	2 1.5K/mm ³ without GCSF
Hemoglobin (Hgb)	2 9 g/dL (without transfusion)
Lymphocyte Count	2 500/ μ L
Platelet Count	2 100,000/ μ L without transfusion
Renal	
Calculated creatinine clearance	2 50 cc/min
OR	
Serum Cr	< 1.5 x institutional ULN
Hepatic	
Bilirubin	< 1.5 \times upper limit of normal (ULN)
Aspartate aminotransferase (AST)	< 2 \times ULN without liver metastasis < 5 \times ULN with liver metastasis
Alanine aminotransferase (ALT)	< 2 \times ULN without liver metastasis < 5 \times ULN with liver metastasis

¹ Cockcroft-Gault formula will be used to calculate creatinine clearance

² Patients with known Gilbert disease who have serum bilirubin level < 3x ULN may be enrolled

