Hepatic event, Grade 3 or 4	
Permanently discontinue atezolizumab.^cConsider patient referral to gastrointestinal specialist for evaluation and liver biopsy to establish etiology of hepatic injury.Initiate treatment with 1–2 mg/kg/day oral prednisone or equivalent.If event does not improve within 48 hours after initiating corticosteroids, consider adding an immunosuppressive agent.If event resolves to Grade 1 or better, taper corticosteroids over \geq 1 month.

Event	Management
In patients with HCC	
AST/ALT is within normal limits at baseline and increases to $> 3 \times \text{ULN}$ to $\leq 10 \times \text{ULN}$ or AST/ALT is $> \text{ULN}$ to $\leq 3 \times \text{ULN}$ at baseline and increases to $> 5 \times \text{ULN}$ to $\leq 10 \times \text{ULN}$ or AST/ALT is $> 3 \times \text{ULN}$ to $\leq 5 \times \text{ULN}$ at baseline and increases to $> 8 \times \text{ULN}$ to $\leq 10 \times \text{ULN}$	
 Monitor LFTs more frequently until return to baseline values. Withhold atezolizumab for up to 12 weeks after event onset.^a 
Events of > 5 days' duration:
 
 Consider initiating treatment with corticosteroids equivalent to 1–2 mg/kg/day oral prednisone. If event resolves to baseline or to Grade 1 or better, resume atezolizumab.^b If event does not resolve to baseline or to Grade 1 or better while withholding atezolizumab, permanently discontinue atezolizumab and contact Sponsor-Investigator.^c
AST or ALT increases to $> 10 \times \text{ULN}$ or total bilirubin increases to $> 3 \times \text{ULN}$	
 Permanently discontinue atezolizumab and contact Sponsor-Investigator.^c Consider patient referral to GI specialist for evaluation and liver biopsy to establish etiology of hepatic injury. Initiate treatment with corticosteroids equivalent to 1–2 mg/kg/day oral prednisone. If event does not improve within 48 hours after initiating corticosteroids, consider adding an immunosuppressive agent. If event resolves to baseline, taper corticosteroids over ≥ 1 month.

LFT = liver function tests.

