^a Atezolizumab may be withheld for a longer period of time (i.e., > 12 weeks after event onset) to allow for corticosteroids (if initiated) to be reduced to ≤ 10 mg/day oral prednisone or equivalent. The acceptable length of the extended period of time must be based on assessment of benefit-risk by the investigator and in alignment with the protocol requirement for duration of treatment and documented by the investigator. Sponsor-Investigator is available to advise as needed.

^b If corticosteroids have been initiated, they must be tapered over ≥ 1 month to ≤ 10 mg/day oral prednisone or equivalent before atezolizumab can be resumed.

^c Resumption of atezolizumab may be considered in patients who are deriving benefit and have fully recovered from the immune-related event. The decision to rechallenge patients with atezolizumab should be based on investigator's assessment of benefit-risk and documented by the investigator (or an appropriate delegate). Sponsor-Investigator is available to advise as needed

GASTROINTESTINAL EVENTS

Immune-mediated colitis has been associated with the administration of atezolizumab. All events of diarrhea or colitis should be thoroughly evaluated for other more common etiologies. For events of significant duration or magnitude or associated with signs of systemic inflammation or acute-phase reactants (e.g., increased C-reactive protein, platelet count, or bandemia): Perform sigmoidoscopy (or colonoscopy, if appropriate) with colonic biopsy, with three to five specimens for standard paraffin block to check for inflammation and lymphocytic infiltrates to confirm colitis diagnosis.

Management Guidelines for Gastrointestinal Events (Diarrhea or Colitis)

Event	Management
Diarrhea or colitis, Grade 1	
 Continue atezolizumab. Initiate symptomatic treatment. Endoscopy is recommended if symptoms persist for > 7 days. Monitor closely.
Diarrhea or colitis, Grade 2	
 Withhold atezolizumab for up to 12 weeks after event onset.^a Initiate symptomatic treatment. Patient referral to GI specialist is recommended. For recurrent events or events that persist >5 days, initiate treatment with 1–2 mg/kg/day oral prednisone or equivalent. If event resolves to Grade 1 or better, resume atezolizumab.^b If event does not resolve to Grade 1 or better while withholding atezolizumab, permanently discontinue atezolizumab.^c

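### Section 6.2 and the Appendix I hepatic table give different permanent-stop rules for Grade 3-4 liver events in patients with liver metastasis and Grade 2 baseline AST/ALT, and the recovery targets also conflict

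*Combined protocol and SAP*

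**What the plan says.** **Eligibility.** Section 3.1, item 10, caps AST and ALT at 2 × ULN without liver metastasis but at 5 × "ULN with liver metastasis". Patients with raised enzymes and liver metastasis are thus admitted on purpose.

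**Section 6.2, stopping.** Grade 3-4 hepatotoxicity ends atezolizumab permanently, "with the exception of patients with liver metastasis who began treatment with Grade 2 AST or ALT". For that group the sentence goes on to discontinue "if AST or ALT increases by greater than or equal to 50% relative to baseline and lasts for at least 1 week". Separately, atezolizumab is withheld for drug-related non-hematological toxicity of at least "Grade 3 including laboratory abnormalities, and severe or life-threatening AEs as below and as listed in appendix".

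**Section 6.2, recovery.** For patients who stay on drug after a Grade 3, Grade 4 or persistent Grade 2 atezolizumab-related event, "dosing should be held until the AE resolves to Grade 0-1 or baseline". A laboratory event still at Grade 2 after 12 weeks may continue if the site and sponsor-investigator agree and it is symptom-free and under control. A later paragraph of the same section permanently stops drug for held, persistent Grade 2 reactions that have not reached Grade 0-1 within 12 weeks of the last dose. It does not mention baseline.

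**Appendix I, Hepatic Events.** The row "Hepatic event, Grade 3 or 4" calls for a permanent stop with no liver-metastasis exception. For Grade 2 events of more than 5 days, drug is withheld and resumed at Grade 1 or better; otherwise, "If event does not resolve to Grade 1 or better while withholding atezolizumab, permanently discontinue atezolizumab". Footnote c allows discretionary rechallenge after either stop. The only rows that take baseline AST/ALT into account are headed "In patients with HCC".

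**The concern.** Section 6.2 sends the reader to Appendix I for detailed management and then states a hepatic exception that Appendix I does not carry. A site treating a patient with liver metastasis whose AST rises from Grade 2 to Grade 3 finds a baseline-relative trigger in one place and a grade-only trigger in the other. No sentence says which prevails.

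For that patient the difference is between a hold that can end at baseline and a permanent stop. Across the trial, atezolizumab exposure in this subgroup, and the toxicity reported under a secondary objective, would depend partly on which page a site consulted. A patient who starts at Grade 2 because of liver metastases may also never reach Grade 1, so whether baseline counts as recovery decides whether treatment can resume.

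**Working it through.** The plan gives no figure to reproduce. The check is a comparison of the texts, then a short calculation of where they diverge.

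**Side by side, for a patient with liver metastasis and Grade 2 AST/ALT at the start of treatment**

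| Situation | Section 6.2 | Appendix I hepatic table |
|---|---|---|
| Grade 3-4, rise below 50% or shorter than 1 week | No permanent stop; if drug-related, withheld until Grade 0-1 or baseline | Permanent stop; footnote c rechallenge possible |
| Grade 3-4, rise of 50% or more for 1 week or more | Discontinued | Permanent stop; footnote c rechallenge possible |
| Worsening within Grade 2 for more than 5 days, then back to the Grade 2 baseline | One paragraph accepts baseline after a hold; another requires Grade 0-1 within 12 weeks; a third allows continuation by agreement for some laboratory events | Withheld, then permanent stop because Grade 1 is not reached; footnote c rechallenge possible |

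The first and third rows conflict; the second agrees on ending treatment. The duration limb of the first row needs no grade cut-offs: a Grade 3 event that resolves in under a week meets the Appendix I stop but not the Section 6.2 trigger.

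**Where the levels diverge**

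Inputs: baseline *b* in multiples of ULN, limited to 5 by Section 3.1; Section 6.2 trigger level = 1.5 × *b*. Assumption: Grade 2 is >3 to 5 × ULN and Grade 3 is >5 × ULN. The documents name CTCAE v5 but give no AST/ALT cut-offs.

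The level conflict for Grade 3 is the interval from 5 to 1.5*b*. It exists only when *b* > 5/1.5 = 3.33.

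| Baseline (× ULN) | 1.5 × baseline | Grade 3 conflict interval |
|---|---|---|
| 3.2 | 4.8 | none by level |
| 3.5 | 5.25 | 5 to 5.25 |
| 4.0 | 6.0 | 5 to 6.0 |
| 4.5 | 6.75 | 5 to 6.75 |
| 4.9 | 7.35 | 5 to 7.35 |

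- Grade 3 example: 4.0 to 5.5 × ULN is 5.5/4.0 − 1 = 37.5%. Section 6.2 does not permanently stop; Appendix I does.
- Grade 2 example: 3.2 to 4.5 × ULN is 4.5/3.2 − 1 = 40.6%. If it lasts more than 5 days and falls back only to 3.2, Appendix I ends in a permanent stop; the Section 6.2 answer depends on which of its paragraphs is read.
- Sensitivity: if Grade 3 began at 6 × ULN, the level conflict would need *b* > 6/1.5 = 4.0, and at 4.5 would run from 6 to 6.75. If grades were read relative to an abnormal baseline, these ULN figures would not apply. The textual conflict and its duration limb would remain.

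**How many patients.** The documents give no rates. Assuming 25-50% have liver metastasis and 3-10% of those start at Grade 2: 60 × 0.25 × 0.03 = 0.45, and 60 × 0.50 × 0.10 = 3.

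**The case against.** The best defence is that Section 6.2 is the specific rule and overrides a general table, that Section 6.1 lets investigators adapt the dose-modification guidelines, and that footnote c makes the Appendix I stop reversible. None of this settles the matter. Section 6.2 itself defers to the Appendix and states no precedence. Section 6.1 gives discretion without saying which text is the starting point. Footnote c requires full recovery, which is undefined for a patient whose baseline is Grade 2.

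Other parts of the defence stand, and they rule out stronger readings that a reader might infer:

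- *That Section 6.2 keeps such patients on drug through Grade 3.* For drug-related events it withholds the dose, so the contrast is hold against permanent stop.
- *That the two texts give opposite steroid instructions.* Section 6.2 gives no instruction to start steroids for hepatic events; the Appendix I instruction is unmatched, not contradicted.
- *That Appendix I takes drug away for purely disease-related enzymes.* The Appendix addresses toxicity at least possibly due to atezolizumab and asks for neoplastic causes to be considered. Section 11.2.3 treats a pre-existing condition as an adverse event only if it worsens. A stable Grade 2 baseline alone triggers nothing.
- *That Section 6.2 is stricter for baselines below 3.33 × ULN.* This applies the 50% clause within Grade 2, although its sentence opens with Grade 3-4 events. The text does not establish that reach.
- *That the HCC rows can never apply.* Inclusion item 9 allows a stable second malignancy needing no treatment, and no exclusion names HCC.

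**Conclusion.** The conflict is real but narrower than a treat-versus-stop contradiction. For Grade 3-4 hepatic events below the 50%/1-week threshold, in patients with liver metastasis and Grade 2 baseline AST/ALT, Section 6.2 does not permanently discontinue and Appendix I does. Recovery targets conflict as well, both between the two places and within Section 6.2.

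This rests on the wording alone. The ULN intervals depend on the assumed cut-offs, and the 0.5 to 3 patients on assumed rates; both are illustrations. Sample size, power and alpha are unaffected. The point merits correction because it concerns permanent withdrawal of the study drug in a group the protocol chose to admit.

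**What to change.** Reconcile the hepatic and recovery paragraphs of Section 6.2 with the Appendix I hepatic table and its footnotes, so that one rule governs patients with liver metastasis and elevated baseline AST/ALT. State in both places:

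- whether the exception applies;
- which trigger ends treatment;
- whether return to baseline counts as recovery, including for the 12-week limit in Section 6.2 and for the full recovery required by footnote c.

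Also say whether the HCC rows are meant to apply in this trial. The sponsor's clinical team decides which rule stands; the request is for one consistent text. The cost is wording in one section and one appendix table at the next amendment, with no added procedures or patients.
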